1.4.2 CT-011 Clinical Studies

A Phase 1, open-label, dose-escalation study was conducted in 17 hematological malignancy patients⁵⁰: eight acute myeloid leukemia (AML) patients, four non-Hodgkin's lymphoma (NHL)

patients, three chronic lymphocytic leukemia (CLL) patients, one Hodgkin's disease (HD) patient, and one multiple myeloma (MM) patient. The purpose of the study was to evaluate the safety, pharmacokinetics, clinical response, and maximum tolerated dose (MTD) of CT-011 (0.2, 0.6, 1.5, 3.0, and 6.0 mg/kg). Most patients had failed several lines of conventional chemotherapy and radiotherapy as well as allogeneic (n=6) or autologous (n=3) stem cell transplantation prior to their enrollment to the study. Eleven of the patients were females and six were males, with an average age of 61 (20–77) years. Sixteen were Caucasian and one Middle-Eastern. In this study, CT-011 was found to have an acceptable safety profile at all dose levels, and was overall well tolerated with no observed serious/unexpected treatment-related adverse events and no observed infusion-related responses. The most common adverse event was diarrhea, which was detected in one low-dose patient (0.2 mg/kg) and one patient treated at the 3 mg/kg dose level. No single dose MTD could be established in this study. Apparent clinical responses were observed in six of the patients 12 months after treatment with CT-011: one complete remission (NHL - follicular lymphoma), four stable disease (HD, 2 CLL, and MM), and one minimal response (AML: platelet-transfusion-independency for 11 months post treatment). Transient elevations in the percentage of peripheral blood CD4+ lymphocytes were observed at 24 hours post CT-011 treatment in 15 of the patients.

A phase II study of CT-011 in combination with rituximab in patients with relapsed follicular lymphoma has been completed. CT-011 given to patients with diffuse large B-Cell lymphoma following autologous stem cell transplant showed increases in specific CD4+ effector/memory T-lymphocytes⁵¹. The study has been completed and results and analysis of progression free survival are forthcoming.

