5.1.3 Route and Method of Administration

CT-011 will be administered intravenously on day 3 of a 28 day cycle.

CT-011 is to be administered intravenously using a peripheral line or a central device if such has been inserted. Patients will be dosed on a mg/kg basis.

The first time CT-011 is to be administered intravenously at a dose of 1.5/3.0/6.0mg/kg delivered over approximately 2 hours as follows:

1. Initial rate of infusion is 50 mL/hr for 30 minutes; If no symptoms related to infusion appear:
2. Increased rate to 100 mL/hr; for 30 minutes; If no symptoms appear:
3. Increased rate to 150 mL/hr for 30 minutes; If no symptoms appear:
4. Increase rate to 200 mL/hr for 30 minutes;

In the event that Grade 3 or higher infusion-related toxicity occurs during infusion, administration of CT-011 should be stopped immediately. Administration of CT-011 could be resumed only after the toxicity has resolved using the slowest rate of infusion (50mL/hr). Once the infusion is resumed, vital signs will be checked every 15 minutes for the first hour, then every 30 minutes till the end of the infusion and then one hour from end of infusion.

If no drug related or infusion related adverse events occur during the first administration, further CT-011 administrations could be delivered over approximately 1:15 hours at a rate of 200mL/hr. Subsequent administrations should be made as scheduled in the absence of Grade 3 or higher adverse events or disease progression.

The maximal administration rate is approximately 250 mg/hr. The total dose administered and the dosing rate will be documented in the patient's medical records.

To ensure complete delivery of CT-011, the IV infusion line must be flushed with 0.9% sodium chloride. The following are two recommended methods for flushing the CT-011 IV infusion line:

- 1) When the CT-011 infusion is complete, add an additional 50mL of 0.9% sodium chloride for

injection to the CT-011 infusion bag. Continue the infusion until a volume equal to that of the volume contained in the tubing has been administered.

- 2) Replace the empty CT-011 infusion bag with a 50mL bag of 0.9% sodium chloride for injection and infuse a volume equal to the volume contained in the tubing. Please note: the flush is not included in the total recommended infusion times.

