5.8.5 Schedule for correlative studies

Laboratory correlative studies will be obtained at screening, days 3, 4, 6, 10 and 17 of cycle 1, days 3 of subsequent cycles and off study. Off-study correlates should be obtained at the time the patient is removed from protocol for any reason. In addition, continued T-cell correlate will be done at 1,3, and 6 months after removal from study. Specimens obtained include BM aspirate (10-15 ml in green-top tubes using heparinized syringe) and peripheral blood (Three-10 ml green top tubes, 2 for cells and 1 for plasma).

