5.8.6 Schedule of Events^a

Investigations	Screening	C1D3	C1D4	C1D6	C1D10	C1D17	C2D3	C3D3	C5D3	CxD3	End of Tx ^b	Follow Up ^p
History, physical examination, concomitant medication review	X	X					X	X		X	X	
Informed written consent	X											
Confirmation of disease relapse and prior treatment	X											
Skeletal survey (CT or MRI as clinically indicated) ^c	X										X	
MUGA or ECHO	X											
β-hCG ^d	X	X										
Toxicity evaluation	X	X					X	X		X	X	X
CBC / differential / platelets ^e	X	X					X	X	X	X ^f	X	
PTT, INR, TSH ^e	X											
BMP, glucose, magnesium ^e	X	X					X	X		X		
LFTs	X	X					X	X		X		
Beta 2 microglobulin ^g	X							X			X	
12-lead ECG ^h	X							X				
Serum monoclonal protein assessments ⁱ	X	X ⁱ					X ⁱ	X ⁱ		X ⁱ	X ⁱ	
24hr urine for creatinine clearance	X											
24hr urine monoclonal protein and immunofixation ^j	X	X ^j					X ^j	X ^j		X ^j	X ^j	
BM biopsy, unilateral ^k	X								X ^k		X ^k	
CT-011 Given		X					X	X	X	X		
Prescribe lenalidomide via RevAssist ^l	X											
T-cell, NK-cell, and CD14 Correlative studies ^m	X	X	X	X	X	X	X	X	X	X	X	X

CT-011 PK ⁿ		X	X	X	X	X	X				
ADA (immunogenicity) ^o	X										

- a. With the exception of PK samples, all other time points have a +/- 4 day window to accommodate weekends, holidays, and for patient convenience.
- b. Off study correlates will be done. In addition, continued T-cell correlate will be done at 1,3, and 6 months after removal from study
- c. Skeletal survey will be done at baseline and may be done at evidence of progression of disease. CT scan will be done to document size of plasmacytoma if this is the only measurable disease.
- d. Female patients of childbearing potential (FCBP, defined in section 8.5) must have a negative pregnancy test (β -hCG) as required by the RevAssist program. Lenalidomide and dexamethasone will start on day 1 of each cycle. Patients do not need to be in clinic to initiate this as all patients would have been exposed to both. Lenalidomide will be ordered for the next cycle. A pregnancy test (urine or serum β -HCG) will also be ordered at this time. Patients must have a negative β -HCG result prior to starting lenalidomide on day 1 of each cycle.

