- e. CBC d/p will be monitored biweekly in cycles 1 to 4, then monthly thereafter. Chemistry tests, including electrolytes, glucose and serum creatinine, should be performed every 2 weeks during the first 2 months of therapy and once a month thereafter. Serum electrolyte monitoring should include potassium, magnesium and calcium. PTT, INR and TSH will be checked every 2 months.
- f. CBC/d/p should also be checked on day 17 of a cycle where lenalidomide's dose has been escalated.
- g. Beta 2 microglobulin will be done after every 2 cycles and at evidence of progression of disease.
- h. Baseline and periodic ECGs should be performed during treatment as indicated in the flow chart. In patients who have ECG abnormalities, ECGs should be performed more routinely as clinically indicated. ECGs post-baseline should be performed as indicated
- i. Myeloma monoclonal protein assessments (Serum protein electrophoresis & immunofixation, immunoglobulin levels, serum free light chain assay) will be performed on day 3 of each cycle (when patients come in for CT-011 infusion) as well as off study.
- j. 24hr urine monoclonal protein assessment (Urine protein electrophoresis & immunofixation) will be performed at screening and as required for response assessment.
- k. Unilateral bone marrow (BM) biopsy will be done at baseline and at end of 4th cycle and evidence of progression for patients with non secretory multiple myeloma
- l. Lenalidomide must be prescribed through and in compliance with Celgene's RevAssist® program. Prescriptions must be filled within 7 days. Any unused lenalidomide should be returned to the patient for disposition in accordance with the RevAssist® program.
- m. T-cell, NK-cell, and CD14 correlates will be collected prior to CT-011 dosing on C1D3, C1D4, C1D6, C1D10, C1D17 and then on Day 3 of all subsequent cycles. T-cell correlates only will also be collected at 1, 3, and 6 months after discontinuation of protocol therapy.
- n. Samples for CT-011 PK determination will be collected in cycle 1 prior to CT-011 infusion, immediately at the end of the infusion, 1 hour after end of infusion, approximately 24(C1D4), 72(C1D6), 168 (C1D10) & 336 (C1D17) hrs – and just prior to next (cycle 2) infusion. Off-study correlates should be obtained at the time the patient is removed from protocol for any reason.

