9.2 LENALIDOMIDE (Revlimid™)

Lenalidomide (REVLIMID®), a thalidomide analogue, is an immunomodulatory agent with anti-angiogenic properties. The chemical name is 3-(4-amino-1-oxo 1,3-dihydro -2H-isoindol-2-yl) piperidine-2,6-dione. Lenalidomide has been studied extensively in myeloma and it is approved for use in newly diagnosed and in relapsed MM.

Supply: REVLIMID® (lenalidomide) is available in 5, 10, 15 and 25 mg capsules for oral administration. Each capsule contains lenalidomide as the active ingredient and the following inactive ingredients: lactose anhydrous, microcrystalline cellulose, croscarmellose sodium, and magnesium stearate. The 5 mg capsule shell contains gelatin, titanium dioxide and black ink. The 10 mg capsule shell contains gelatin, FD&C blue #2, yellow iron oxide, titanium dioxide and black ink.

Elimination: The metabolic profile of lenalidomide in humans has not been studied. In healthy volunteers, approximately two-thirds of lenalidomide is eliminated unchanged through urinary excretion. The process exceeds the glomerular filtration rate and therefore is partially or entirely active. Half-life of elimination is approximately 3 hours.

Pregnancy: Due to its structural similarities to thalidomide, a known human teratogen, lenalidomide is contraindicated in pregnant women and women capable of becoming pregnant. When there is no alternative, females of childbearing potential may be treated with lenalidomide provided adequate precautions are taken to avoid pregnancy. Females must commit either to abstain continuously from heterosexual sexual intercourse or to use two methods of reliable birth control, including at least one highly effective method (e.g., IUD, hormonal contraception, tubal ligation, or partner's vasectomy) and one additional effective method (e.g., latex condom, diaphragm, or cervical cap), beginning 4 weeks prior to initiating treatment with REVCLIMID® (lenalidomide), during therapy with REVCLIMID® (lenalidomide), during therapy delay, and continuing for 4 weeks following discontinuation of REVCLIMID® (lenalidomide) therapy. If hormonal or IUD contraception is medically contraindicated, two other effective or highly effective methods may be used.

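### The +/- 4 day window in note a does not protect the nominal timing of the cycle 1 immune samples, above all those labelled C1D4 and C1D6

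*Combined protocol and SAP*

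**What the plan says.** Section 5.1.3 sets time zero: "CT-011 will be administered intravenously on day 3 of a 28 day cycle". Section 5.8.5 lists the immune sampling days: "Laboratory correlative studies will be obtained at screening, days 3, 4, 6, 10 and 17 of cycle 1". Note m to section 5.8.6 repeats them: "T-cell, NK-cell, and CD14 correlates will be collected prior to CT-011 dosing on C1D3, C1D4, C1D6, C1D10, C1D17".

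Note a then sets the tolerance, "With the exception of PK samples, all other time points have a +/- 4 day window", and gives the reason, "to accommodate weekends, holidays, and for patient convenience". Sections 5.8.4, 5.8.5 and 8.1 to 8.4 and note m set no tighter limit for the immune samples around their post-infusion days.

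Note n ties the PK samples carrying the same day labels to hours after infusion: "approximately 24(C1D4), 72(C1D6), 168 (C1D10) & 336 (C1D17) hrs". Nothing requires the immune blood to be drawn at the same time as the PK blood.

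Pharmacodynamics of CT-011 is a secondary endpoint (section 2.4). Section 6.1.2 describes the correlative analyses as exploratory. Section 8.2 compares the pre-treatment level of tumor-reactive T cells with the highest level seen after therapy.

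**The concern.** Sampling at 1, 3, 7 and 14 days after an infusion makes sense only if the samples can be told apart in time. A tolerance of 4 days either side is wider than the 1 and 2 day gaps between days 3, 4 and 6, and equal to the 4 day gap between days 6 and 10. A sample can meet the protocol and still carry a label that says little about when it was drawn.

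The early samples have a purpose that depends on timing. The protocol's account of the earlier single-agent study of 17 patients reports: "Transient elevations in the percentage of peripheral blood CD4+ lymphocytes were observed at 24 hours post CT-011 treatment in 15 of the patients". If a similar short-lived change occurs here, blood drawn before the infusion or five days after it, but labelled C1D4, could miss it. An absence of early change could then not be told apart from late or early drawing. The pre-treatment versus peak comparison is exposed as well, because a peak that falls between actual draws is never observed. Mistimed samples cannot be recovered afterwards.

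**Working it through.** **Inputs.** Infusion on day 3 (section 5.1.3). Immune sampling days 3, 4, 6, 10 and 17 (section 5.8.5, note m). Tolerance 4 days either side (note a). PK times about 24, 72, 168 and 336 h (note n).

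**The plan's own mapping.** Hours after infusion = (day − 3) × 24. Day 4 gives 24, day 6 gives 72, day 10 gives 168 and day 17 gives 336. These match note n, so the day labels and the PK hours agree.

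**Permitted days.** Window = nominal day − 4 to nominal day + 4, which is 9 calendar days. Day 0 is the day before cycle day 1.

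| Label | Permitted days | Hours from a day 3 infusion | Days before the infusion day |
|---|---|---|---|
| C1D4 | 0 to 8 | −72 to +120 | 3 (days 0, 1, 2) |
| C1D6 | 2 to 10 | −24 to +168 | 1 (day 2) |
| C1D10 | 6 to 14 | +72 to +264 | 0 |
| C1D17 | 13 to 21 | +240 to +432 | 0 |

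For C1D3, note a alone would allow days −1 to 7. Note m reasonably confines that sample to before the infusion, so it is left out of the table.

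**Overlap (whole days shared, of 9).**
- C1D4 and C1D6: days 2 to 8, which is 7.
- C1D6 and C1D10: days 6 to 10, which is 5.
- C1D4 and C1D10: days 6 to 8, which is 3.
- C1D10 and C1D17: days 13 and 14, which is 2.

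Blood drawn on day 6, 7 or 8 is therefore valid under three labels: C1D4, C1D6 and C1D10. The order can also reverse: a C1D6 sample on day 2 and a C1D4 sample on day 8 both comply.

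**Tolerance that would keep the labels apart.** Two windows of half-width w do not overlap if 2w is less than the gap. The largest whole-day values are 0 for the 1 day gap (days 3 to 4), 0 for the 2 day gap (days 4 to 6), 1 for the 4 day gap (days 6 to 10) and 3 for the 7 day gap (days 10 to 17). The plan's value is 4 throughout.

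**A second wording problem.** Read literally, note m asks for samples before CT-011 dosing on days 4, 6, 10 and 17 of cycle 1, although CT-011 is given only on day 3. The phrase can apply only to day 3 samples.

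**The case against.** The strongest reply is that the visits are already fixed. C1D4 and C1D6 are named in section 5.8.5, have their own columns in the schedule and appear in note m, and the exempt PK draws bring the patient in at about 24 and 72 h. Sites may well take both tubes together. This stands against a reading that a reader might infer, namely that the early time points do not exist. They do exist; what is missing is any rule that holds the immune blood to them.

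A reader might also try to state what share of an early signal is lost. That needs the rate at which the immune effect fades and the spread of actual draw times, and the documents give neither. The only CT-011 half-life given, 270 to 410 h in section 1.4.2, is a drug level and not an effect.

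A further inference would be that the day 3 sample of later cycles could fall on or off lenalidomide, since section 9.2 says: "Half-life of elimination is approximately 3 hours". The documents do not support this. That figure describes elimination from the body, and nothing states how long the effect on T or NK cells lasts. Note i places the day 3 visit at the CT-011 infusion, and note m can be read as placing those samples before it, so the sample travels with the infusion.

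It is also fair that no analysis is planned at a nominal C1D4 or C1D6. Sections 8.1 to 8.4 work mainly from baseline, each cycle and the peak, and the 24 h CD4+ finding is background and not a hypothesis of this trial. This limits the harm but does not remove it, because the peak and any plot of early change depend on when blood was drawn.

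Finally, immune blood goes to a central laboratory for cell processing (section 5.8.4), while PK serum can be frozen and held (Appendix G). A fixed PK visit does not guarantee weekend handling of cells. That is a real cost.

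**Conclusion.** The point holds as a fault in a stated rule: note a permits immune samples whose label does not fix their time relative to the infusion. Its size is 7 of 9 days shared between C1D4 and C1D6, and a permitted range of −72 to +120 h for a nominal 24 h sample. These figures describe what the text allows, not what sites will do; real draws will probably cluster near the PK visits. The hours assume that the infusion takes place on day 3. If that visit also moved under note a, the calendar overlaps would stand but the hours would shift.

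The consequence is confined to early pharmacodynamics. A reader might infer a threat to the main results. The MTD rule and the cut-offs of at most 9 and at least 12 responses in 29 do not use these samples. One qualification applies: with 10 or 11 responses, section 6.1.2 brings correlative outcomes into the final judgement, without saying which. From the plan's own error rates, that zone has probability 1 − 0.83 − 0.04 = 0.13 at a true response rate of 25% and 1 − 0.87 − 0.03 = 0.10 at 50%. The change is worth making because it is cheap and protects a named secondary endpoint.

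**What to change.** - In note a, extend the PK exemption to the cycle 1 T-cell, NK-cell and CD14 samples, and have them drawn with the same day's PK sample: before the infusion on C1D3, then at about 24, 72, 168 and 336 h.
- Reword note m so that drawing before CT-011 applies only to the day 3 sample of each cycle.
- Record the date and time of every immune draw and of the infusion, and analyse cycle 1 immune data by actual time from infusion.

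If the laboratory needs some leeway, 1 day either side at C1D10 and C1D17 creates no overlap; C1D4 and C1D6 leave no room for it.

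The change adds no patient, tube or visit. It costs scheduling freedom for these samples, and the processing laboratory must be able to receive fresh blood from all sites on the days concerned, including weekends and holidays when they fall there. Confirm this with the laboratory before the footnote is amended.

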4.2 Definition of Dose Limiting Toxicity

For the phase I portion, patients will be monitored for safety by assessing toxicities as graded by the NCI CTCAE v4.0. The maximum tolerated dose (MTD) or dose limiting toxicity (DLT) will be defined as one or more of the following toxicities considered to be at least possibly related to one of the study drugs during Cycle 1:

- Grade 3 or greater non-hematologic toxicity with the exception of Grade 3 nausea, vomiting and diarrhea that responds to supportive therapy.
- Grade 4 thrombocytopenia, or grade 3 thrombocytopenia with bleeding, or any requirement for platelets transfusion

- Grade 4 neutropenia persisting for more than 5 days.
- Grade 3 or greater febrile neutropenia (temperature $\geq 38.5^{\circ}\text{C}$)
- Grade 4 anemia, unexplained by underlying disease

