5.2 Lenalidomide (RevlimidTM)

5.2.1 Lenalidomide Administration and Schedule

Lenalidomide will be given orally. Schedule as shown in table 5.1

The first dose level starts at 15 mg days 1-21 of a 28 day cycle.

If a dose is missed or vomited up, the dose will not be made up.

Beginning by day 1 of cycle #2 and on day 1 of every cycle thereafter, while all six conditions below have been met, patients will be evaluated for lenalidomide dose escalation.

For patients that:

- Never had a lenalidomide dose reduction due to a toxicity that was probable or definitely related to lenalidomide.
- Maintained platelet count $\geq 50,000$ at all times in the previous cycle
- Minimum ANC $\geq 1,000$ at all times in the previous cycle
- No clinically significant grade 2 or greater non-hematologic toxicities in the previous cycle
- Not yet reached the maximum daily dose of 25 mg of lenalidomide
- Are willing to undergo dose escalation of lenalidomide.
- Serum Creatinine maintained at ≤ 2 mg/dL as in initial eligibility

Then the patient's dose for lenalidomide will be increased by 5 mg per cycle for days 1-21 of a 28 day cycle. If any of the criteria are not met, then no lenalidomide dose escalations will occur during this cycle.

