5.3.1 Table 5.1 Adverse events and Dose Adjustment of drugs

Neutropenia	Grade 3 or greater on day 1 of cycle: delay and monitor CBC weekly; if resolves to \leq grade 2 within 4 weeks, resume lenalidomide with 5mg dose reduction. If grade 3 or greater during a cycle, hold lenalidomide for the remainder of the cycle. Resume with 5mg dose reduction for subsequent cycles. G-CSF or GM-CSF are not to be used to avoid dose reductions but can be used for treatment of febrile neutropenia
Febrile Neutropenia	Hold lenalidomide for the remainder of the cycle. Consider G-CSF administration until there is adequate count recovery $ANC \geq 1000/\mu L$ + absence of fever. If neutropenia resolves \leq grade 2, resume lenalidomide at 5 mg dose reduction for subsequent cycles.
Thrombocytopenia	If grade 3 or greater, hold lenalidomide for the remainder of the cycle and until platelets $\geq 50,000/\mu L$. Then resume lenalidomide at 5 mg dose reduction for subsequent cycles.
Anemia	For grade 3 or greater, hold lenalidomide for the remainder of the cycle and until hemoglobin recovers to \leq grade 2.
Fatigue (asthenia, malaise) Lenalidomide or dexamethasone	For intolerable grade 2 or grade 3-4, hold the protocol therapy thought to be probable or definitely related to the reaction until resolves to \leq grade 1, then resume protocol therapy with dose reduction of implicated protocol therapy by one dose level (5 mg for lenalidomide and/or 50% for dexamethasone).
Rash Lenalidomide	If grade 3 or greater, hold lenalidomide until resolves to \leq grade 2, then resume protocol therapy. In the instance of intolerable recurrent rash, stop implicated drug but may continue on study.
Renal insufficiency	For patients with calculated or measured GFR $<30\text{ml/min}$, lenalidomide should be held until creatinine returns to baseline
Venous Thromboembolism	All protocol should be held until the patient is adequately anti-coagulated. Patients with recurrent thrombosis despite adequate anti-coagulation should be removed from protocol therapy.
Suspected Pregnancy	Protocol therapy should be held until pregnancy is ruled out. Discontinue all protocol therapy if pregnancy is positive
Dyspepsia, gastric or duodenal ulcer, gastritis Grade 1-2 (requiring medical management)	Treat with H2 blockers, sucralfate, or omeprazole. If symptoms persist despite above measures, decrease dexamethasone dose by 1 dose level

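### The Cycle 1 blood-count schedule is inconsistent and, on its likelier reading, too sparse to ascertain the plan's own hematologic DLTs

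*Combined protocol and SAP*

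**What the plan says.** Section 4.2 counts DLTs in Cycle 1 only. One is defined by duration: "Grade 4 neutropenia persisting for more than 5 days". Another is grade 4 thrombocytopenia, which needs a single value; grade 3 with bleeding, or a need for platelet transfusion, also counts.

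The counts that feed these criteria are set in 5.8.6:

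- **Table.** The row "CBC / differential / platelets" is marked at screening, C1D3, C2D3 and later visits. C1D4, C1D6, C1D10 and C1D17 are blank, although 5.8.5 has blood drawn then: "Laboratory correlative studies will be obtained at screening, days 3, 4, 6, 10 and 17 of cycle 1".
- **Footnote e.** "CBC d/p will be monitored biweekly in cycles 1 to 4, then monthly thereafter". No days are given. Its next sentence uses other words for chemistry: "Chemistry tests, including electrolytes, glucose and serum creatinine, should be performed every 2 weeks during the first 2 months of therapy".
- **Footnote a.** "With the exception of PK samples, all other time points have a +/- 4 day window".
- **Footnote f.** It adds a day 17 count only in a cycle with a lenalidomide escalation. Under 5.2.1 escalation is first considered for Cycle 2, so this cannot apply in Cycle 1.

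Table 5.1 (5.3.1) says "delay and monitor CBC weekly" for neutropenia present on day 1 of a cycle. For a grade 3 or worse value during a cycle it holds lenalidomide but gives no repeat interval. Section 5.6 requires ANC and platelet thresholds on Day 1 of each new cycle, with weekly evaluation if they are not met. Nothing says how to classify a single grade 4 ANC of unknown duration.

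**The concern.** A criterion of more than 5 days can be applied only if counts are close enough to show when grade 4 begins and ends. The table alone leaves 28 days between Cycle 1 counts, and the footnote leaves 14 days or about 3 to 4, depending on how one word is read. Sites that read it differently would ascertain DLTs differently in cohorts of 3 to 6 patients.

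The MTD is the phase I primary endpoint and sets the phase II dose. A DLT that is not recorded is handled as no DLT, and in a 3+3 design that favors escalation. The same sparse counts bear on 5.2.1, where platelets and ANC must have held "at all times in the previous cycle".

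**Working it through.** The plan states no detection probability or 3+3 operating characteristic, so there is no figure of its own to reproduce.

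**Spacing.** Nominal every-2-weeks counts fall on days 3, 17 and 31. With windows of 4 days either side, gaps run from 14 − 8 = 6 to 14 + 8 = 22 days. By the table alone the gap is 28 days (20 to 36 with windows).

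**Chance that an episode is sampled at all.** A count on day c falls in an episode of L days if onset lies in (c − L, c]. With onset uniform over a range (my assumption), the probability is the part of that range covered, divided by its width. For L = 6, day 17 covers onset days 11–17, day 31 covers 25–31, and a day 29 count (implied by 5.6) covers 23–29.

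| Onset range (width) | Table only: D3, D31 | Every 2 weeks: D3, D17, D31 | Every 2 weeks plus D29 |
|---|---|---|---|
| days 5–22 (17) | 0/17 = 0 | 6/17 = 0.35 | 6/17 = 0.35 |
| days 4–28 (24) | 3/24 = 0.125 | 9/24 = 0.375 | 11/24 = 0.46 |
| days 8–28 (20) | 3/20 = 0.15 | 9/20 = 0.45 | 11/20 = 0.55 |

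A 10-day episode is sampled with probability 0.71 (onset days 4–28) or 0.80 (days 8–28) on D3, D17 and D31.

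**Chance that duration is shown.** Two grade 4 values more than 5 days apart are needed. At exact spacing d, the chance that two counts fall in an episode is max(0, (L − d)/d), up to L = 2d.

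- d = 14: zero for any L below 14. A day 29 count lies 12 days after day 17, so it helps only above 12 days (0.08 to 0.10 at L = 14).
- d = 7: 0 at L = 6, 1/7 = 0.14 at L = 8, 3/7 = 0.43 at L = 10. Weekly counts can show the duration of longer episodes.
- Twice weekly (D3, 6, 10, 13, 17, 20, 24, 27, 31): every episode of 4 days or more is sampled, and a 10-day neutropenia is shown to exceed 5 days with probability about 0.70.

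**Effect on escalation.** With observed DLT rate q, P(escalate) = (1 − q)³ + 3q(1 − q)⁵, which falls as q rises. The true rates and missed fractions below are assumptions.

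| True DLT rate | None missed | 1/16 missed | 1/4 missed | 9/16 missed |
|---|---|---|---|---|
| 0.33 | 0.43 | 0.48 | 0.61 | 0.83 |
| 0.40 | 0.31 | 0.35 | 0.49 | 0.76 |

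The fractions are hematologic share times share of those missed: 1/4 × 1/4, 1/2 × 1/2 and 3/4 × 3/4. For a true rate of 0.40 with a quarter missed, q = 0.30 and 0.343 + 0.9 × 0.168 = 0.49.

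**Effect of marking C1D10 and C1D17.** Day 10 covers onset days 4–10. For L = 6, on D3, D10, D17 and D31, sampling rises from 6/17 to 11/17 = 0.65 (days 5–22), from 9/24 to 15/24 = 0.625 (days 4–28) and from 9/20 to 11/20 = 0.55 (days 8–28). A further count near day 24 gives 15/17 = 0.88, 21/24 = 0.875 and 17/20 = 0.85. Counts on D4 and D6 add nothing: on the first two ranges the onset days they reach are already covered by day 10 (day 6 covers 0–6), and on the third they fall before the range.

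**The case against.** The strongest reply is that biweekly may mean twice weekly. Footnote e uses different words for chemistry in the next sentence, which can suggest a different interval. Nor does the blank at day 17 decide it: the table also omits day 17 for chemistry, which the footnote plainly sets at every 2 weeks. This stands as an ambiguity. Every 2 weeks is still likelier, because a window of 4 days either side exceeds the spacing of twice-weekly counts and the next step down is monthly. If twice weekly was meant, the table leaves out nearly all the counts.

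A reader might infer that the schedule cannot detect hematologic DLTs at all. The documents do not support that. One scheduled count can show grade 4 thrombocytopenia, and bleeding with grade 3 or a transfusion need also counts. Visit windows can bring two counts to 6 days apart. A late episode may be caught by the Day 1 check for Cycle 2 and the weekly follow-up in 5.6 and Table 5.1. Unscheduled counts are not barred. Detection is incomplete, not absent.

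A reader might also infer that the MTD is biased upward as a fact, citing the 13% and 41% grade 3/4 myelosuppression in 1.3.1. Those rates come from 30 mg per day in total, above this trial's 15 to 25 mg, and are not limited to a first cycle. The same study's times to first clinically significant grade 3/4 myelosuppression, 1.8 and 5.5 months, fall after the 28-day DLT window. And if a single grade 4 ANC of unknown duration were counted as a DLT, the error would run the other way.

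**Conclusion.** The point holds as a defect of ascertainment. Table and footnote do not agree on when Cycle 1 counts are taken, and no rule covers repeat counts after a mid-cycle grade 4 value or an unknown duration.

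On the every-2-weeks reading, a 6-day grade 4 episode is sampled about 35% to 46% of the time, or 55% with late onset and a day 29 count. At nominal spacing, scheduled counts cannot show that a neutropenia shorter than 14 days lasted more than 5 (shorter than 12 if a day 29 count is taken). Short grade 4 platelet nadirs can be missed.

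These figures assume uniform onset, nominal days and no unscheduled counts. For undetected DLTs the direction is certain: escalation becomes more likely. How far the MTD would move is unknown, because the documents give no Cycle 1 grade 4 rate or episode length; the escalation figures are illustrations. On the twice-weekly reading most of the gap closes, and what remains is the contradiction with the table and the missing classification rule.

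**What to change.** 1. In the 5.8.6 table, mark a CBC at C1D10 and C1D17, where blood is already drawn. Sampling of a 6-day episode rises from 35% to about 65% with onset over days 5–22, and from 45% to 55% with onset over days 8–28. A further count near day 24 would give about 88% (85% on the later range), but it is an extra visit, so the sponsor should weigh it.
2. In footnote e, replace biweekly with an interval in days, and make the table agree.
3. Days 10 and 17 are 7 days apart and do not by themselves settle a 5-day criterion. Reconcile 4.2, Table 5.1 and 5.8.6 so that the plan states the repeat-count interval after a grade 4 ANC and how an episode of unknown duration is classified. The sponsor should choose that rule and fix it in advance.
4. Reconcile the condition in 5.2.1, "at all times in the previous cycle", with the CBC schedule.

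The cost is one extra tube at existing draws, repeat counts in the few patients with a grade 4 value, and edits to the table and footnotes. Slightly more DLTs may be recorded.
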